8.3.10.1 Maternal Exposure

Pregnancy itself is not regarded as an AE unless there is a suspicion that the IMP under study may have interfered with the effectiveness of a contraceptive medication. Congenital anomalies/birth defects and spontaneous miscarriages should be reported and handled as SAEs. Elective abortions without complications should not be handled as AEs. The outcome of all pregnancies (spontaneous miscarriage, elective termination, ectopic pregnancy, normal birth or congenital anomaly/birth defect) should be followed up and documented even if the participant was discontinued from the study.

If any pregnancy occurs in the course of the study, then the Investigator or other site personnel informs the appropriate AstraZeneca representatives within **1 day**, ie, immediately but **no later than 24 hours** of when he or she becomes aware of it.

The designated AstraZeneca representative works with the Investigator to ensure that all relevant information is provided to the AstraZeneca Patient Safety data entry site **within 1 or 5 calendar days** for SAEs (see Section [8.3.9](#)) and **within 30 days** for all other pregnancies.

The same timelines apply when outcome information is available.

The PREGREP module in the eCRF is used to report the pregnancy and the paper-based PREGOUT module is used to report the outcome of the pregnancy.

8.3.10.2 Paternal Exposure

In case of pregnancy of the partner of a male participant, the partner's pregnancy should be reported on the pregnancy form (consent from the partner must be obtained before the pregnancy form is completed) following the same timeframe and routing as described for any participant's pregnancy. Pregnancy of the participant's partner is not considered to be an AE. These pregnancies will also be followed up, and the outcome of the pregnancy (spontaneous

miscarriage, elective termination, ectopic pregnancy, normal birth, or congenital abnormality) should, if possible, be obtained and documented.

8.3.11 Medication Error, Drug Abuse, and Drug Misuse

8.3.11.1 Timelines

If an event of medication error, drug abuse, **or** drug misuse occurs during the study, then the Investigator or other site personnel informs the appropriate AstraZeneca representatives within **one calendar day**, ie, immediately but **no later than 24 hours** of when they become aware of it.

The designated AstraZeneca representative works with the Investigator to ensure that all relevant information is completed within **1** (Initial Fatal/Life-Threatening or follow-up Fatal/Life-Threatening) **or 5** (other serious initial and follow-up) **calendar days** if there is an SAE associated with the medication error (see Section [8.3.9](#)) and **within 30 days** for all other medication errors.

8.3.11.2 Medication Error

For the purposes of this clinical study a medication error is an **unintended** failure or mistake in the treatment process for an IMP or AstraZeneca NIMP that either causes harm to the participant or has the potential to cause harm to the participant.

The definition of a Medication Error can be found in [Appendix B 4](#).

8.3.11.3 Drug Abuse

Events of drug abuse with IMP or AstraZeneca NIMP are collected in all studies where drug abuse is possible.

For guidance, refer to AstraZeneca SOP ‘Management of Individual Case Safety Reports (ICSR) in Clinical Trials’, SOP-0108717.

Drug abuse is the persistent or sporadic **intentional**, non-therapeutic excessive use of IMP or AstraZeneca NIMP for a perceived reward or desired non-therapeutic effect.

The full definition and examples of drug abuse can be found in [Appendix B 4](#).

8.3.11.4 Drug Misuse

Events of drug misuse with IMP or AstraZeneca NIMP are collected in all studies where drug misuse is possible.

For guidance, refer to AstraZeneca SOP ‘Management of Individual Case Safety Reports (ICSR) in Clinical Trials’, SOP-0108717.

Drug misuse is the **intentional** and inappropriate use (by a study participant) of IMP or AstraZeneca NIMP for medicinal purposes outside of the authorized product information, or for unauthorized IMPs or AstraZeneca NIMPs, outside the intended use as specified in the protocol and includes deliberate administration of the product by the wrong route.

The full definition and examples of drug misuse can be found in [Appendix B 4](#).

8.4 Overdose

For this study, any dose of AZD7442 greater than a planned weight-based dose presented in [Table 6](#) will be considered an overdose.

AstraZeneca does not recommend a specific treatment for an overdose. Symptoms of overdose should be treated as per clinical judgment.

- An overdose with associated AEs is recorded as the AE diagnosis/symptoms on the relevant AE modules in the eCRF and on the Overdose eCRF module.
- An overdose without associated symptoms is only reported on the Overdose eCRF module.

If an overdose on an AstraZeneca study intervention occurs during the study, the Investigator or other site personnel inform appropriate AstraZeneca representatives immediately, but **no later than 24 hours** of when he or she becomes aware of it.

The designated AstraZeneca representative works with the Investigator to ensure that all relevant information is provided to the AstraZeneca Patient Safety data entry site **within one or 5 calendar days** for overdoses associated with an SAE (see [Section 8.3.9](#)) and **within 30 days** for all other overdoses.

8.5 Human Biological Samples

Instructions for the collection and handling of biological samples will be provided in the study specific Laboratory Manual. Samples should be stored in a secure storage space with adequate measures to protect confidentiality. For further details on Handling of Human Biological Samples see [Appendix C](#).

Samples will be stored for a maximum of 15 years from the date of the issue of the CSR in line with consent and local requirements, after which they will be destroyed.

- Pharmacokinetic samples will be disposed of after the Bioanalytical Report finalization or 6 months after issuance of the draft Bioanalytical Report (whichever is earlier), unless consented for future analyses.

- Pharmacokinetic samples may be disposed of or anonymized by pooling. Additional analyses may be conducted on the anonymized, pooled PK samples to further evaluate and validate the analytical method. Any results from such analyses may be reported separately from the CSR.
- Remaining ADA sample aliquots will be retained at AstraZeneca or its designee for a maximum of 15 years following issue of the CSR. Additional use includes but is not limited to further characterization of any ADAs, confirmation and/or requalification of the assay as well as additional assay development work. The results from future analysis will not be reported in the CSR.

8.5.1 Total Blood Volume

Blood volume estimates are provided in **Table 16**. For participants other than neonates, the total estimated blood volume to be collected during the study is approximately 73 mL per participant. For neonates, only safety and PK samples will be collected and the total estimated blood volume to be collected during the study is approximately 22 mL per participant. The total volume can be adjusted by age and the body weight of the participant per local ethics requirements. Where necessary, the visit windows in the SoA can be used to collect samples across a number of days. When sample collection occurs over ≥ 2 days for a given study visit, participants are required to visit the site at least once per study visit. If practical, additional sample collection can take place at home visits as long as the samples are obtained per protocol by qualified personnel. If it is not possible to obtain sufficient blood from a participant at a given study visit, the order of the samples will be prioritized according to the key requirements of the study and the following hierarchy will be applied: safety (ie, serum chemistry, hematology, coagulation), PK, SARS-CoV-2 neutralizing antibodies, and ADA (see Laboratory Manual). For participants receiving IV infusions of AZD7442, blood samples are to be collected from the opposite side of the body to the IV infusion at Visit 1.

Table 16 Blood Volume Estimates

Visit (study day \pm visit window)	Estimated blood volume for neonates ^a	Estimate blood volume for all other participants ^b
Screening Visit (Day -7 to Day 0)	3.7 mL	6.3 mL
Visit 1 (Day 1 \pm 0)	1.2 mL (IV only)	6.0 to 8.5 mL ^{c, d}
Visit 2 (Day 4 to 15 \pm 2)	1.2 mL	2.5 mL
Visit 3 (Day 31 + 5)	4.9 mL ^e	14.8 mL
Visit 4 (Day 92 \pm 5)	2.6 mL ^e	10.3 to 12.8 mL ^d
Visit 5 (Day 183 \pm 10)	3.5 mL ^e	13.0 mL
Visit 6 (Day 366 \pm 15)	4.9 mL ^e	14.8 mL
Total from screening to Day 366	20.8 to 22.0 mL	67.7 to 72.7 mL

^a For neonates, only safety and PK samples will be collected.

^b For participants other than neonates, the following hierarchy will apply if it is not possible to obtain blood for all samples: (1) safety, (2) pharmacokinetics, (3) SARS-CoV-2 neutralizing antibodies, and (4) anti-drug antibodies.

^c At Visit 1, participants receiving AZD7442 IV will have an extra 2.5mL blood sample taken for post-dose PK sampling.

^d At Visit 4, participants in Cohort 1 will also have an additional 2.5mL taken for SARS-CoV-2 serology.

^e For Visits 3 to 6 blood samples should be taken on at least 2 different days and at least 24 h apart

Blood samples can be taken on different days within the sampling window specified in the Schedule of Activities (Section 1.3).

COVID-19, coronavirus disease 2019; IM, intramuscular; IV, intravenous; PK, pharmacokinetic; SARS-CoV-2, severe acute respiratory syndrome coronavirus 2.

Repeat blood samples may be collected for safety reasons.

8.5.2 Pharmacokinetics

- Serum samples will be collected for measurement of serum concentrations of AZD7442 (AZD8895 and AZD1061) at either Day 4, 8, 11, or 15 (one sample) and Days 31, 92, 183, and 366 (one sample on each day), as specified in the SoA (Section 1.3). For participants who receive AZD7442 via an IV infusion, a serum sample should also be taken at the end of the infusion on Day 1 from the opposite side of the body. Serum samples should still be taken even if the participant is outside the visit window specified in the SoA.
- Samples may be collected at additional time points during the study if warranted and agreed upon between the Investigator and the Sponsor, eg, for safety reasons. The timing of sampling may be altered during the course of the study based on newly available data (eg, to obtain data closer to the time of peak or trough matrix concentrations) to ensure appropriate monitoring.
- Serum samples will be used to assess the PK of AZD7442 following IM and IV administration. Samples collected for analyses of AZD7442 serum concentration may also be used to evaluate safety or efficacy aspects related to concerns arising during or after the study.
- Samples will be collected, labeled, stored, and shipped, as detailed in the Laboratory Manual.
- AZD7442 PK parameters (eg, maximum serum concentration, AUC), if data permit, will be calculated based on AZD7442 serum concentrations following IM and IV administration.

8.5.2.1 Determination of Drug Concentration in Serum

Samples for determination of drug concentration in serum will be assayed by bioanalytical test sites operated on behalf of AstraZeneca, using an appropriately validated bioanalytical method. The bioanalytical sample results and the analytical method used will be described in a

separate Bioanalytical Report.

8.5.2.2 Determination of Drug Concentration in Nasal Secretions

Nasal samples to measure AZD7442 concentrations in nasal mucosa will be collected when test supplies are available and assessed using an appropriately qualified bioanalytical assay.

8.5.3 Immunogenicity Assessments

Serum samples for immunogenicity assessments will be collected according to the SoA (Section 1.3). Samples will be collected, labeled, stored, and shipped, as detailed in the Laboratory Manual.

8.5.3.1 Anti-drug Antibody

Blood samples for determination of ADA in serum will be assayed using an appropriately validated bioanalytical method. The results and the method details will be described in a separate report.

8.5.3.2 SARS-CoV-2 Serology

Serum samples will be collected to assess SARS-CoV-2 antigen-specific antibody levels at baseline from all participants. Serostatus will also be collected from non-neonates in Cohort 1 according to the SoA (Table 3). Baseline serostatus and time to seroconversion in participants receiving AZD7442 will be determined using a validated SARS-CoV-2 nucleocapsid antigen assay operated by an authorized laboratory. Serologic assessment to S (spike), RBD, and nucleocapsid antigens may also be assessed quantitatively using a validated multiplexed meso scale discovery immunoassay.

8.5.4 Pharmacodynamics: Neutralizing Antibody Assessments

8.5.4.1 SARS-CoV-2 Neutralizing Antibody Assessments

Serum samples to measure SARS-CoV-2 neutralizing antibody titers will be collected from participants according to the time points specified in the SoA (Section 1.3). Authorized laboratories may measure neutralizing antibodies to SARS-CoV-2 using validated wild-type live virus or pseudovirus neutralization assays.

For storage, re-use, and destruction of pharmacodynamic samples, see Section 8.5 and Appendix C.

8.6 Human Biological Sample Biomarkers

8.6.1 Virologic Assessments

Instructions for obtaining and processing samples for RT-PCR are provided in the Laboratory Manual. A SARS-CoV-2 rapid antigen test can be performed at each site at screening to enable same-day assignment to study cohorts. During the study, samples will also be assessed by authorized RT-PCR assays for the detection of SARS-CoV-2 by the central laboratories

according to the time points specified in the SoA (Section 1.3). Unscheduled RT-PCR testing may be performed in participants in Cohort 1 who present with COVID-19 qualifying symptom(s) (Section 8.1.1).

For Cohorts 2 and 3, viral load will be assessed in samples collected on Day 1 (at the site) and on Day 8 (at the site or at home) by an authorized RT-PCR assay for the quantitative measurement of SARS-CoV-2. The type of sample (eg, saliva, blood, nasopharyngeal) should be consistent between all study visits for each participant, but particularly for the samples collected on Day 1 and Day 8 which will be used to estimate the change in viral load.

8.6.2 Other Study-related Biomarker Research

Already collected samples may be analyzed for different biomarkers thought to play a role in COVID-19 severity or outcomes, including, but not limited to, serum, plasma or mucosal cytokines, quantification of RNA, micro-RNA, and/or non-coding RNA, using quantitative RT-PCR, microarray, sequencing, or other technology in blood, saliva, or mucosal specimens to evaluate their association with observed clinical responses to AZD7442. Other study-related biomarker research excludes genetic analysis.

For storage, re-use, and destruction of biomarker samples, see Section 8.5 and Appendix C.

8.7 Optional Genomics Initiative Sample

Collection of optional samples for Genomics Initiative research are out of scope for pediatric studies.

8.8 Medical Resource Utilization and Health Economics

Medical resource utilization and health economics are not applicable in this study.

9 STATISTICAL CONSIDERATIONS

9.1 Statistical Hypotheses

No hypotheses are planned in this PK, PD, safety study.

9.2 Sample Size Determination

Approximately 120 participants will be screened/enrolled to achieve 100 evaluable participants.

Note: “Enrolled” means a participant’s, or their legally acceptable representative’s, agreement to participate in a clinical study following completion of the informed consent process. Potential participants who are screened for the purpose of determining eligibility for the study, can be rescreened once. If they are not subsequently assigned to receive AZD7442 in the study, they are considered “screen failures”.

The total sample size of 100 participants across all pediatric age groups is the minimum number required to adequately characterize the AZD7442 safety profile in pediatric participants following IM or IV administration (based on FDA feedback). Furthermore, preliminary PK simulations based on adult PK data determined that with a minimum sample size of 24 participants ($n = 6$, per route of administration, in the 4 age groups from any cohort), and the proposed PK sampling scheme, 80% of the simulated trials estimated the geometric mean for CL with a 95% confidence interval that remained within 60% to 140% of the point estimate in each pediatric subgroup.

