## 2 CHANGES TO PROTOCOL PLANNED ANALYSES

A summary of adverse events by maximum intensity was planned in protocol Section 9.4.4. This was removed per AZD7442 program-level data presentation decision.

Enrolment into the study has been discontinued due to FDA feedback. No participant has been included for Cohort 3, and the full analysis set will contain 46 instead of 100 participants. Planned analyses for Cohorts with no participants will not be conducted.

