**Table 1: Analysis sets**

Population/Analysis Set	Description
Screened Population Set (SPS)	All participants who signed the ICF. Unless otherwise stated, this set will be used for the presentation of disposition data.
Full Analysis Set (FAS)	All participants who received the IMP, irrespective of their protocol adherence and continued participation in the study. Participants who withdraw consent or assent to participate in the study will be included up to the date of their study termination.
Modified Full Analysis Set (mFAS)	All participants who are in the FAS, excluding participants who were assigned to Cohort 1 by rapid COVID-19 test, but have a positive confirmatory test.
Safety Analysis Set (SAF)	All participants who have received IMP.
PK Analysis Set (PKS)	All participants who received AZD7442 and from whom PK blood samples are assumed not to be affected by factors such as protocol violations, and who had at least one quantifiable serum PK observation post-dose, will be included in the PK analysis dataset.
AZD1061 ADA Evaluable Analysis Set (ADS1)	A participant is AZD1061 ADA evaluable if in the SAF and having a non-missing baseline AZD1061 ADA result and at least one non-missing post-baseline AZD1061 ADA result.
AZD8895 ADA Evaluable Analysis Set (ADS2)	A participant is AZD8895 ADA evaluable if in the SAF and having a non-missing baseline AZD8895 ADA result and at least one non-missing post-baseline AZD8895 ADA result.
AZD7442 ADA Evaluable Analysis Set (ADS3)	All participants who are AZD8895 ADA evaluable and/or AZD1061 ADA evaluable.
SARS-CoV-2 nAb Evaluable Analysis Set (SES)	All participants in the Safety Analysis Set from whom blood samples were assumed not to be affected by factors such as protocol violations, and who had at least one quantifiable serum titer observation post dose.

Generally, all listings will be prepared based on the SAF unless otherwise stated.  
Disposition data will be listed for the SPS.

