### **Analysis of Adverse Events**

The safety of AZD7442 will primarily be assessed by:

- Incidence of TEAEs through end of study
- Incidence of SAEs through end of study
- Incidence of AESIs through end of study

Summaries of these incidences will include the number and percentage of participants reporting at least one event with the 95% exact Clopper-Pearson confidence interval for the percentage, number of events, exposure adjusted rates and presented by cohort and route of administration.

An overview of AEs will be presented for each cohort and route of administration, including the number and percentage of participants with any AE and SAEs. Summaries will present the relationship to IMP as assessed by the Investigator, seriousness, and deaths.

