D8850C00006 Open-label, Uncontrolled, Single dose Study to Evaluate the Pharmacokinetics, Pharmacodynamics, and Safety of AZD7442 in Pediatric Participants Aged $\geq$ 29 Weeks Gestational Age to < 18 Years	IM and IV; dose is dependent on cohort indication and participant's weight. PK samples collected at end of infusion (IV only), on either 3, 7, 10 or 14 days post-dose, and then 28, 91, 182, and 365 days post-dose	~100 a	Phase I, pre-exposure prophylaxis, Treatment of COVID-19 in non-hospitalized participants, Treatment of COVID-19 in hospitalized participants

a The enrolment for this study was stopped early due to FDA feedback, therefore the full analysis set will only contain 46 participants.

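### The protocol's stated safety minimum of 100 becomes 46 in the SAP, with no statement that it is unmet and no AE interval specified for all dosed participants together

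*Protocol*

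**What the plan says.** Safety and tolerability is a co-primary objective (Protocol Section 3). On size, Protocol 9.2 says: "The total sample size of 100 participants across all pediatric age groups is the minimum number required to adequately characterize the AZD7442 safety profile". It attributes the number to FDA feedback and plans recruitment to reach it: "Approximately 120 participants will be screened/enrolled to achieve 100 evaluable participants". No event rate, interval width or detection probability accompanies the 100, and Protocol 9.1 confirms that the study is descriptive: "No hypotheses are planned in this PK, PD, safety study".

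SAP Section 2, which lists changes to the planned analyses, reports the stop and its result: "Enrolment into the study has been discontinued due to FDA feedback", and "the full analysis set will contain 46 instead of 100 participants". The footnote to SAP Table 5 repeats that "the full analysis set will only contain 46 participants". The only analytical consequence given is that analyses for cohorts without participants, which means Cohort 3, will not be run.

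For AEs, SAP 4.2.2.1 asks for the number and percentage of participants with at least one TEAE, SAE or AESI, with the "95% exact Clopper-Pearson confidence interval for the percentage", by cohort and route of administration.

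On the denominator, SAP Table 1 defines the Safety Analysis Set (SAF) as "All participants who have received IMP", and SAP Table 2 assigns the safety endpoints to it. The opening text of SAP 4.2.2 instead bases the safety summaries on the SARS-CoV-2 nAb Evaluable Analysis Set (SES).

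**The concern.** The plan names a size below which it does not regard safety as adequately characterised, and then analyses fewer than half that number. The SAP is where the consequence should be recorded, because Protocol 9.4.1 sends deviations and additional analyses there. SAP Section 2 records the count and the reason, but not that a stated minimum was missed and not what the remaining number can show.

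The minimum is also a pooled number, set across all age groups, whereas the AE tables are specified only by cohort and route. Elsewhere the SAP asks for an overall result explicitly: disposition is summarised overall and by cohort (4.1.2.2), and the PK summaries include an all-weights category (4.2.1). As written, a reader has no specified interval to set against the 100.

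This matters most for the AESIs, such as anaphylaxis, MIS-C and thrombotic events, where a count of zero is plausible and the upper limit carries the information.

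**Working it through.** **The plan's own figure.** The 100 cannot be derived, because the documents give no rate, precision or power for it. Only its additions can be checked. The columns of Protocol Table 5 give 19 + 12 + 14 + 7 + 16 + 32 = 100, and the age rows give 46 + 18 + 18 + 18 = 100. The 46 in the adolescent row is a coincidence and is not the analysed 46.

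**Safety denominator.** In SAP Table 1 both the Full Analysis Set and the SAF consist of participants who received IMP. If the former has 46, so does the SAF. This assumes that SAP Table 2 (SAF) governs the safety summaries. Under the SES the number could be lower, because that set requires a quantifiable post-dose titer. Neonates give only safety and PK blood samples (Protocol 8.5.1), so any who were enrolled would drop out.

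**Zero-event upper limit.** For the SAP's two-sided 95% Clopper-Pearson interval with no events, the upper limit is 1 − 0.025^(1/n).

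- n = 100: 1 − 0.025^(1/100) = 3.6%
- n = 46: 1 − 0.025^(1/46) = 7.7%

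**Chance of seeing at least one event.** This is 1 − (1 − p)^n, where p is the true rate per participant. The documents give no p, so the rates below are assumptions.

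| Assumed p | n = 100 | n = 46 |
|---|---|---|
| 1% | 1 − 0.99^100 = 63% | 1 − 0.99^46 = 37% |
| 2% | 1 − 0.98^100 = 87% | 1 − 0.98^46 = 61% |
| 3% | 1 − 0.97^100 = 95% | 1 − 0.97^46 = 75% |
| 5% | 1 − 0.95^100 = 99% | 1 − 0.95^46 = 91% |

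The lowest true rate with a 95% chance of at least one event is 1 − 0.05^(1/n), which is 3.0% at 100 and 6.3% at 46.

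**Cells.** The documents do not give the split of the 46 by cohort and route, so no cell figure can be computed from them. The limit 1 − 0.025^(1/n) rises as n falls, so any cell smaller than 46 has a zero-event limit above 7.7%.

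**The case against.** The case against is substantial, and most of its facts stand.

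- **Disclosure.** The drop is reported in the section meant for it, with the reason. Anyone who reads SAP Section 2 beside Protocol 9.2 can see that 46 is below 100. What is missing is the explicit statement and its consequence.
- **Intervals already planned.** A reader might infer that a finding of no events will be taken at the strength of 100 participants. The documents do not support that. SAP 4.2.2.1 requires exact intervals, and SAP 3.3.1 requires each table to show its denominator, so a zero count will carry a limit based on the actual number. Splitting by cohort and route widens intervals and does not overstate certainty.
- **No planned precision.** The 100 is a regulatory figure with no precision target, so the 3.6% limit and the assumed rates are a yardstick supplied here and not a promise that the plan broke. No calculation in the documents is wrong.
- **Regulatory meaning.** Both the 100 and the stop are attributed to FDA feedback, and neither communication is available. Whether the agency still regards 100 as the minimum is unknown.
- **Table shells.** SAP 3.3.1 leaves presentation details to a shells document that is not available. A pooled column may exist there, but the SAP text does not ask for one.

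These points limit the finding without removing it. Intervals within cells neither tell a reader that a stated minimum was missed nor give the pooled estimate to which that minimum refers. A descriptive study rests on its precision, so the absence of hypotheses does not make a statement of precision unnecessary.

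**Conclusion.** The point holds as a gap in reporting and specification. The plan states a pooled safety minimum of 100 and delivers 46, which is 46% of it. It does not say that the minimum is unmet, and it specifies no AE interval for all dosed participants together. The rate that can be excluded when no event is seen roughly doubles, from 3.6% to 7.7%. An event with an assumed true rate of 3% would go entirely unseen with probability 25% at 46 (100 − 75), against 5% at 100 (100 − 95).

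These figures rest on three assumptions: the SAF is the safety denominator, it contains 46 participants, and the event rates are illustrative.

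A reader might go further and conclude that the co-primary safety objective has failed, or that the shortfall was hidden. Neither is supported. The shortfall is stated plainly, and the 100 carries no quantitative criterion against which failure could be judged. The planned exact intervals already provide part of the remedy.

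**What to change.** No further enrolment is asked for.

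1. **Denominator.** Reconcile SAP 4.2.2 (SES) with SAP Table 2 (SAF) so that the safety summaries use the SAF.
2. **SAP 4.2.2.1.** Add a column for all dosed participants (SAF, N = 46) giving the number, percentage and exact 95% interval for TEAEs, SAEs and AESIs, beside the columns by cohort and route.
3. **SAP Section 2.** State that the 100-participant minimum in Protocol 9.2 is not met. Give the zero-event 95% exact upper limit of 7.7% at 46 (3.6% at 100). Give the chance of at least one event as 75% (against 95%) at an assumed 3% rate and 37% (against 63%) at an assumed 1% rate, labelled as assumptions. Add the corresponding cell figures, computed from the actual cohort and route counts, and require the safety conclusion to be worded to match.

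The cost is one extra table column, a paragraph, and a stated figure less favourable than the one for 100. No analysis planned by cohort or route is lost.
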